APPENDIX VI: RECTAL SWAB COLLECTION FOR MICROBIOME ANALYSIS

OPTION 1: Flocked Swabs & Plastic Applicator - Reagents and Supplies Needed:

Regular flocked swab, plastic applicator, sterile in dry tube (Copan, catalog #552C)

Protocol:

1. Remove swab from plastic tube. Hold the swab by the end of the plastic handle and take care not to touch the cotton tip of the swab to any surfaces or with fingers.
2. Insert the swab through the rectal sphincter and approximately 3 cm into the anal canal. Rotate the swab and withdraw.
3. Place the swab back into the plastic tube.

OPTION 2: Peel-Pouch Swabs - Reagents and Supplies Needed:

- Regular flocked swab, plastic applicator, sterile in peel pouch (Copan, catalog #519CS01)
- Sterile 15mL conical tube
- Pair of purple nitrile powder free exam gloves
- Biohazard collection bag

Protocol:

1. Put on purple nitrile gloves.
2. Remove swab from peel pouch. Hold the swab by the end of the plastic applicator and take care not to touch the cotton tip of the swab to any surfaces or with fingers.
3. Insert the swab directly into the rectum and approximately 3 cm into the anal canal. Rotate the swab and withdraw. **If fecal matter is on the swab, it has been done correctly.**
4. Place the swab into the 15mL conical tube and snap off at the red break-off point. Discard gloves as to not get any material on the outside of the tube.
5. Screw cap back onto tube securely and place tube into biohazard bag.

ALL OPTIONS: The swab samples can be kept at 4°C or -20°C prior to transport to the [name] lab.

APPENDIX VII: Ordering from Invitae

Ordering from Invitae

PLACE YOUR ORDER

Place your order online for the most efficient processing.

1. Create an account by visiting www.invitae.com/signup.
2. Sign in and then click **Start an order**.
3. Under **Test selection**, browse Invitae's panels to select a pre-curated panel or create a **custom test** and add it to your order. You can also select a test from your recent or custom orders; order family follow-up testing; or order through a sponsored testing program or clinical trial by choosing the **Partnership programs** tab.
4. Fill out the requested information, including patient information in any order; save your entries at any time to come back to them later.
5. Enter billing information.
6. Submit your order.

If you prefer to open an account by speaking with an Invitae representative, please contact us at [contact].

COLLECT A SPECIMEN

1. Order Invitae blood or saliva collection kits, which you need for collecting and returning your specimen, at www.invitae.com/request-a-kit.
2. Label the specimen tube with the patient's full name, date of birth, and specimen collection date.
3. If you need additional details on our specimen requirements, please visit www.invitae.com/specimen-requirements.

Continued on back

Ordering from Invitae (*continued*)

PRINT THE REQUISITION FORM

1. Print the requisition form that was created during the online ordering process.
2. If you prefer to place a paper-based order for panel testing, you can also download our paper test requisition from www.invitae.com/order-forms. Please note that exome testing is ordered exclusively online.

SEND THE SPECIMEN AND FORMS TO INVITAE

1. Package the requisition form with your patient's specimen in the provided collection box.
2. You're now ready to call your shipping carrier to schedule a pick-up. Within the US, return shipping is offered at no additional charge and a label is included in the collection kit.
3. We recommend shipping the specimen overnight, on the same day the specimen is collected. We also recommend shipping at the beginning of the week to avoid any transport delays over a weekend.

RESULTS

1. Once Invitae receives the shipment, you will receive the results in:
 - Panel testing: 10–21 calendar days (14 days on average)
 - STAT panel testing: 5–12 calendar days (7 days on average)
 - Exome testing: 20 weeks on average
2. If you ordered online, you can view the status of your order by logging in to your account. Alternatively, if you provided your email address on your paper-based order form, you can create an online account following the steps above to view the status of your order.
3. You will receive a notification email once the test results are ready.

If you have any questions about the ordering process, please contact Client Services at [contact] or [contact]. Local contact information outside the US can be found at www.invitae.com/contact.

APPENDIX VIII: Immunophenotyping

Peripheral blood will be collected into two heparin tubes (green top tubes) according to the study calendar. Following collection, [name] from the [name] lab will be notified for collection (see contact information below). Peripheral blood mononuclear cells (PBMCs) will be isolated using standard protocols of Ficoll isolation and cryopreserved in freezing media (FBS, 10%DMSO). Cells will be stored long-term in liquid nitrogen until thawed for batch analysis. Upon thawing, cells will be immunophenotyped using multiparameter flow cytometry to evaluate the immunologic and metabolic phenotype of the following cell subsets: CD4 and CD8 T cells, FOXP3+ Tregs, B cells, NK cells, monocytes, dendritic cells, and myeloid derived suppressor cells (Table 1). Samples will be run on a Cytek Aurora machine, which allows for the simultaneous detection of up to 25 markers. Additionally, the metabolic fitness of the total PBMCs will be evaluated using the mitochondrial stress test on the Seahorse analyzer. Functional assays will be run on PBMCs to determine the relative capacity of peripheral T cells to metabolically respond to T cell receptor stimulation through activation of CD3 and CD28. Additional vials will be stored for RNA-sequencing of relevant populations identified in initial immunophenotyping.

Contact information

Primary point of contact

[name]

[contact]

[contact]

Secondary point of contact

[name]

[contact]

[contact]

Table 1. Immuno- and metabolic phenotyping of PBMCs

Marker	Purpose
Live Dead	Dead cell exclusion
H3K27me3	Histone Methylation
CTLA4	Immune phenotype-Co-inhibitory
PD1	Immune phenotype-Co-inhibitory
41BB	Immune phenotype-Co-stimulatory
CCR7	Immune phenotype-Memory
CD45RA	Immune phenotype-Memory
Ki67	Immune phenotype-Proliferation

CD19	Immune subset-B cell
CD15	Immune subset-MDSC
CD33	Immune subset-MDSC
HLA-DR	Immune subset-Monocyte/DCs
CD14	Immune subset-Monocyte/MDSC
CD56	Immune subset-NK cell
CD3	Immune subset-T cell
CD4	Immune subset-T cell
CD8	Immune subset-T cell
FOXP3	Immune subset-Treg
CPT1a	Metabolic phenotype-Fatty acid oxidation
GLUT1	Metabolic phenotype-Glycolysis
Hexokinase II	Metabolic phenotype-Glycolysis
LDHA	Metabolic phenotype-Glycolysis
pS6	Metabolic phenotype-mTOR activity
TOMM20	Metabolic phenotype-OXPHOS
VDAC1	Metabolic phenotype-OXPHOS

APPENDIX IX: RAPID SPECT Imaging Sub-Contract Study

Purpose: To measure radiation exposure to specific metastases by performing SPECT scans at 2-4 hours, 24 hours (+/- 4 hours), and 48 hours (+/- 4 hours) following Xofigo infusions #1 and #6 to calculate the total radiation exposure to the specific metastases.

All patients participating in Hopkins Xofigo/XRT (RAVENS) trial will be eligible for participation in the Rapid SBIR-contract supported CX α RPT (companion) trial.

Patient treatment will not change. A data collection effort for retrospective evaluation of results will be conducted by Hopkins via a companion protocol that patients participating in the parent trial may sign on to. The target population is 20 out of the 30-34 patients that will be enrolled in the SABR + Xofigo arm of the RAVENS trial. The expected accrual is 10 patients in year 1 and 10 patients in year 2.

Patients will be compensated with a \$100 gift card for the 3 ^{223}Ra SPECT/CT scans following Xofigo infusion #1, and a \$100 gift card for the 3 ^{223}Ra SPECT/CT scans following Xofigo infusion #6. gift cards and scans will be paid for by the research budget from the NIH sub-contract.

Hypothesis: The ^{223}Ra dosimetry calculations performed will demonstrate, retrospectively, that > 30% of the patients would have required an adjustment in the XRT treatment plan, to meet the following criteria:

[figure not shown]
1. Tumor absorbed dose (to at least 5 lesions) \geq 80 EQD2 -Gy (BED=96 Gy; $\alpha/\beta=10$ Gy),
2. Normal organ doses within tolerance limits.

[figure not shown]
Data/Workflow:

- For patients participating in the RAVENS protocol, Hopkins will collect ^{223}Ra SPECT/CT at 2-4 hours, 24 hours (+/- 4 hours), 48 hours (+/- 4 hours) after first and last Xofigo infusion.
- Rapid receives anonymized SPECT projection data, performs quantitative recon, 3D-RD dosimetry, and provides combined RPT-XRT (CXRPT) dose map to Hopkins.
- Hopkins compares XRT dose map w/ and w/o α RPT dosimetry and determines if a change would have been merited.
- Rapid receives Hopkins assessments.

Standard Operating Procedure
Quantitative Imaging and Dosimetry of Radium-223
V2.2; July 8, 2019

Characteristics of Ra-223	Radium-223 is primarily an alpha emitter (95.3% abundance). The fractions emitted as beta and gamma particles are 3.6% and 1.1%. The gamma component allows for the in-vivo imaging.																																																		
Purpose of imaging procedure	Exploratory – to evaluate variability in Ra-223 uptake across patients and how the proposed combination agents impact this, also how tumor burden impacts distribution and dosimetry.																																																		
Dosage level ¹	As per Xofigo package insert																																																		
Radiation dose to main organs ¹ (Gy/MBq)	

Adrenals	0.00012	

Brain	0.00010	

Breasts	0.00005	

Gallbladder wall	0.00023	

Lower large intestine wall	0.04645	

Small intestine wall	0.00726	

Stomach wall	0.00014	

Upper large intestine wall	0.03232	

Heart wall	0.00173	

Kidneys	0.00320	

Liver	0.00298	

Lungs	0.00007	

Muscle	0.00012	

Ovaries	0.00049	

Pancreas	0.00011	

Red marrow	0.13879	

Osteogenic cells	1.15206	

Skin	0.00007	

Spleen	0.00009	

Testes	0.00008	

Thymus	0.00006	

Thyroid	0.00007	

Urinary bladder wall	0.00403	

Uterus	0.00026	

Whole body	0.02311	

	Adrenals	0.00012	Brain	0.00010	Breasts	0.00005	Gallbladder wall	0.00023	Lower large intestine wall	0.04645	Small intestine wall	0.00726	Stomach wall	0.00014	Upper large intestine wall	0.03232	Heart wall	0.00173	Kidneys	0.00320	Liver	0.00298	Lungs	0.00007	Muscle	0.00012	Ovaries	0.00049	Pancreas	0.00011	Red marrow	0.13879	Osteogenic cells	1.15206	Skin	0.00007	Spleen	0.00009	Testes	0.00008	Thymus	0.00006	Thyroid	0.00007	Urinary bladder wall	0.00403	Uterus	0.00026	Whole body	0.02311
Adrenals	0.00012																																																		
Brain	0.00010																																																		
Breasts	0.00005																																																		
Gallbladder wall	0.00023																																																		
Lower large intestine wall	0.04645																																																		
Small intestine wall	0.00726																																																		
Stomach wall	0.00014																																																		
Upper large intestine wall	0.03232																																																		
Heart wall	0.00173																																																		
Kidneys	0.00320																																																		
Liver	0.00298																																																		
Lungs	0.00007																																																		
Muscle	0.00012																																																		
Ovaries	0.00049																																																		
Pancreas	0.00011																																																		
Red marrow	0.13879																																																		
Osteogenic cells	1.15206																																																		
Skin	0.00007																																																		
Spleen	0.00009																																																		
Testes	0.00008																																																		
Thymus	0.00006																																																		
Thyroid	0.00007																																																		
Urinary bladder wall	0.00403																																																		
Uterus	0.00026																																																		
Whole body	0.02311																																																		
Patient preparation	Nothing beyond what is already specified in the protocol																																																		
SPECT imaging length	~30 mins per FOV																																																		
FOVs taken	Chest & Abdomen, if there are relevant lesions outside these two fields of view then additional views could be collected as needed. After first field is collected, to extent possible, patient should remain on couch for subsequent FOV collection.																																																		

													
Imaging Time points (post-injection)	2-4 hours, 24 hours \pm 4 hours, 48 hours \pm 4 hours												
SPECT Acquisition parameters for SPECT/CT	
 
 Collimator	MEGP	
 
 Matrix	128 x 128	
 
 Time / view	30 seconds/view	
 
 # of projection views	120	
 
 Angle range	360	
 
 Energy Window Setting (KeV)	71.4 96.6 (30% at 84) 138.5 168.5 (20% at 154) 249.7 290.2 (15% at 270)	
 
	Collimator	MEGP	Matrix	128 x 128	Time / view	30 seconds/view	# of projection views	120	Angle range	360	Energy Window Setting (KeV)	71.4 96.6 (30% at 84) 138.5 168.5 (20% at 154) 249.7 290.2 (15% at 270)
Collimator	MEGP												
Matrix	128 x 128												
Time / view	30 seconds/view												
# of projection views	120												
Angle range	360												
Energy Window Setting (KeV)	71.4 96.6 (30% at 84) 138.5 168.5 (20% at 154) 249.7 290.2 (15% at 270)												
CT acquisition parameters for SPECT/CT	The CT portion of the first SPECT/CT scan for each patient should be in high res (i.e., diagnostic mode); attenuation mode (low-dose) may be used for subsequent scans. Standard vendor settings for high resolution/diagnostic vs low-dose or attenuation acquisition may be applied.												
Quality control required	Standard camera quality control (QC) as specified by the vendor should be up to date on all cameras that will be used for this study. Typical QCs include uniformity, linearity/spatial resolution, and center of rotation alignment. Dose calibrator QCs should also be routinely performed and documented (accuracy, consistency, linearity, and geometry).												

Additional requirement	
Sensitivity needs to be measured prior to or immediately after the patient scan. Suspend a calibration source (with known amount of Ra-223 – 2MBq) between the two camera heads (by taping it to a yard stick and supporting the stick on the bed). The source should be such that there are no attenuating materials between, including the bed or meter stick, between the source and collimator. Position the source so it is 15 ± 0.5 cm from the face of each collimator and collect a 5 min dual head single view scan (256x256 matrix, same collimator/energy windows as above).
 
Recommended phantom calibration scan	
There is a recommended phantom calibration scan with either a NEMA PET IEC Body Phantom or an ACR Phantom to be collected for each camera that may be used for Ra-223 patient imaging. This scan is collected once prior to camera's use for Ra-223 patient imaging. The body of the phantom should be filled with water at room temperature removing as much of the air as possible. All spheres must be removed except the largest one. The activity and measurement time of the syringe prepared earlier should be recorded. All the activity (~2 MBq) contained in the syringe should be injected into the largest sphere (a long needle might be needed). Both, activity and measurement time after the injection (with needle on) must be recorded. The rest of the large sphere can be completely filled with water, using a new syringe and needle.
 
The image technician must make sure that the largest sphere is in place before putting the lid on the phantom and hand-tighten the screws.
 
The phantom should be placed flat-side down on the bed (pad can be removed, if necessary) and in the middle of the camera field of view.
 
SPECT and CT images should be acquired using pre-defined patient imaging protocol(s) and parameters used should be recorded.

Reporting requirements	
None, a table of results will be provided for each patient to the institution or to the PI of the protocol with the expectation that this will lead to a publication.

Interpretation for dosimetry (or any other) purpose	
N/A; Results will be analyzed and used for publication to evaluate patient to patient variability and impact of tumor burden. Study will also provide accurate SPECT-imaging based dosimetry.

Step by step imaging procedure	Routine SPECT/CT imaging procedure in clinical practices should be used with the parameters specified above.
Data to send	SPECT projections, attenuation map, and all CT slices (in DICOM format).
Image quantification procedure	SPECT projections will be reconstructed using previously published iterative quantitative reconstruction methods established by Rapid ²⁻⁵ . Volume of interest (VOIs) will be drawn around the major organs and lesions of interest at each time points. Total counts in the VOIs at each time point will be calculated and converted to activity by measured sensitivity. The time integrated activity coefficients (TIACs), mathematically equivalent to the number of decays per unit injected activity, will be calculated from single or double exponential fits for the main source organs and the lesions. The TIACs in the red marrow (TIACRM) will be derived from contours drawn around lumbar vertebrae L3-L5, the TIACRM will be divided by the marrow mass in this region to give TIACRM concentration. Total TIACRM will be obtained as the product of this concentration and the estimated patient RM mass.
Dosimetry analysis procedure	The absorbed dose values for target organs will be derived by using whole organ S-value based method and MC-calculation using images and 3D-RD approach (RBE =5 for alphas). Importantly, Rapid follows SNMMI MIRD Committee recommendations as published in its series of pamphlets and will update calculation accordingly if necessary. Mean absorbed dose (mAD) and mean (mBED) will be obtained using the software package 3D-RD ⁶⁻¹⁰ . The methodology used in 3D-RD is briefly summarized below: 
 1. Using the Electron Gamma Shower (EGS) Monte Carlo (MC) software, one million events will be run for the beta- and photon components of the isotope decay spectra, for each time point. 2. The energy deposition distribution from the contributing components from MC will be weighted for probability and unit activity then converted to absorbed dose rate for each VOI (spectra probability distributions obtained from LBL/Lund web site¹¹). 3. The dose rates for the each VOI will be fitted using the simulation Analysis and Modeling II (SAAM II) software package (The Epsilon Group, Charlottesville VA), and the area under the curve calculated as the absorbed dose mAD. 4. The mBED will be calculated using the linear-quadratic (LQ) BED methodology described in reference¹².

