Radium-223 is a ready-to-use solution and should not be diluted or mixed with any solutions. Each vial is for single use only. Parenteral drug products should be inspected visually for particulate matter and discoloration prior to administration, whenever solution and container permit.

Before the first administration of Xofigo, the absolute neutrophil count (ANC) should be $\geq 1.5 \times 10^9/L$, the platelet count $\geq 100 \times 10^9/L$ and hemoglobin $\geq 10 \text{ g/dL}$. Before subsequent administrations of Xofigo, the ANC should be $\geq 1 \times 10^9/L$ and the platelet count $\geq 50 \times 10^9/L$. If ANC is not within normal limit prior to protocol window, then CBC can be drawn, per treating physician advisement. All doses 6 doses should still be administered regardless of

treatment delay due to ANC. Unless, there is no recovery to these values within 6 to 8 weeks after the last administration of Xofigo, despite receiving supportive care, then further treatment with Xofigo should be discontinued. Patients with evidence of compromised bone marrow reserve should be monitored closely and provided with supportive care measures when clinically indicated. Discontinue Xofigo in patients who experience life-threatening complications despite supportive care for bone marrow failure.

Dosage:

The dose regimen of radium-223 is 50 kBq (1.35 microcurie) (55 kBq/kg (1.49 microcurie/kg) after implementation of the NIST update) per kg body weight, given at 4 week intervals for 6 injections.

The volume to be administered to a given patient should be calculated using the:

- Patient's body weight (kg)
- Dosage level 50 kBq/kg body weight (55 kBq/kg after implementation of the NIST update) or 1.35 microcurie/kg body weight (1.49 microcurie after implementation of the NIST update)
- Radioactivity concentration of the product (1,000 kBq/mL; 27 microcurie/mL (1,100 kBq/mL after implementation of the NIST update; 29.7 microcurie/mL) at the reference date
- Decay correction factor to correct for physical decay of radium-223.

The total amount (volume to be drawn into the syringe) to be administered to a patient should be calculated as follows:

Volume to be administered (mL) =
Body weight (kg) x dose (50 kBq/kg b.w)^a/
DK factor x 1,000 kBq (0.027 mCi)/mL^b

^a 55 kBq/kg after implantation of the NIST update

^b 1,100 kBq (29.7 microcurie)/mL after implantation of the NIST update

Decay Correction Factor Table

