Days from Reference Date	Decay Factor	Days from Reference Date	Decay Factor
-14	2.296	0	0.982
-13	2.161	1	0.925
-12	2.034	2	0.870
-11	1.914	3	0.819
-10	1.802	4	0.771
-9	1.696	5	0.725
-8	1.596	6	0.683
-7	1.502	7	0.643
-6	1.414	8	0.605
-5	1.330	9	0.569
-4	1.252	10	0.536
-3	1.178	11	0.504
-2	1.109	12	0.475
-1	1.044	13	0.447
		14	0.420

The Decay Correction Factor Table is corrected to 12 noon Central Standard Time (CST). To determine the decay correction factor, count the number of days before or after the reference date. The Decay Correction Factor Table includes a correction to account for the 7 hour time difference between 12 noon Central European Time (CET) at the site of manufacture and 12 noon US CST, which is 7 hours earlier than CET.

Immediately before and after administration, the net patient dose of administered radium-223 should be determined by measurement in an appropriate radioisotope dose calibrator that has been calibrated with a National Institute of Standards and Technology (NIST) traceable radium-223 standard (a new reference vial will be sent to each center corresponding to the updated NIST reference material) and corrected for decay using the date and time of calibration. The dose calibrator must be calibrated with nationally recognized standards, carried out at the time of commissioning, after any maintenance procedure that could affect the dosimetry and at intervals not to exceed one year.

Each center must perform the Radium Ra 223 dichloride dial setting on their relevant dose calibrator(s) (upon notification by Bayer each center is required to update the dial setting to correspond to the new NIST standard). The current dial settings are to remain in effect until Bayer obtains FULL approval from the FDA for implementation. In preparation for implementation of the NEW dial setting, the clinical study center will receive a sealed vial labeled NIST standard containing a Radium Ra 223 dichloride solution for calibration only. The vial is identical to the vials used for study treatment. The amount of Radium Ra 223 dichloride in the vial will be stated on the label. Instructions for the dial setting, including the calibration log form, will be enclosed with the dispatch of the calibration sample.

NIST Standardization Update:

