6.6 Drug Accountability

Study drugs should be kept in a secure place and must be administered only to patients in the trial. A log of study drug (received, administered to patients and destroyed) must be maintained and signed by the person responsible for drug handling at each center. Study site/institution personnel will record all study drug administered during this trial on the drug-dispensing log. Description of monitoring of the overall drug accountability will be detailed in study and site specific procedures.

The nuclear medicine specialist or radiation oncologist at the center is responsible for drug accountability for radium-223. When the drug accountability has been monitored, the vials can be destroyed in accordance with hospital procedure for the handling of radioactive material, normally after storage for 4 months from date of receipt (>10 half-lives) before disposal; they may then be disposed as non-radioactive waste.

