6.11 Criteria for Patient Removal

Diagnosis of >3 bone and/or soft tissue metastases on entry imaging studies before SBRT/SABR. PSA >50 ng/ml before SABR. Progression as defined in section 9.5.5.

Radium-223 administration may be delayed by no more than four weeks for recovery of adverse events. In case of a treatment delay greater than four weeks, treatment should be discontinued. It is important to note that in general (unless otherwise agreed), in cases where study drug has been ordered, the time window is reduced to -3 days to + 3 days, due to decay. If administration has to be postponed more than 3 days after drug has been ordered, replacement of the drug order is required. Dose reduction for radium-223 will not be permitted and subjects with any toxicity requiring radium-223 dose reduction must discontinue radium-223 treatment.

Any toxicity requiring radium-223 discontinuation will be recorded as an AE in the subject's medical record and on the CRF.

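### Appendix IX does not say how radium left from infusions #1–5 is handled in the infusion #6 scans; uncorrected, the #6 coefficient is about 22% too high in a physical-decay base case

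*Combined protocol and SAP*

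**What the plan says.** Section 6.4 sets radium-223 dosing as "given at 4 week intervals for 6 injections" and prints a Decay Correction Factor Table running from day -14 to day +14. Section 6.11 allows delays of up to four weeks and says that, once drug has been ordered, "the time window is reduced to -3 days to + 3 days".

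Appendix IX describes a companion imaging study of about 20 men in the SABR + Radium-223 arm. Its purpose is stated as "performing SPECT scans at 2-4 hours, 24 hours (+/- 4 hours), and 48 hours (+/- 4 hours) following Xofigo infusions #1 and #6", in order "to calculate the total radiation exposure to the specific metastases". There are two dose routes:

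- **TIAC route (image quantification procedure).** Counts in each volume of interest are totalled at each time point and turned into activity using the measured camera sensitivity. The TIACs, "mathematically equivalent to the number of decays per unit injected activity, will be calculated from single or double exponential fits", are then obtained for source organs and lesions.
- **3D-RD route (dosimetry analysis procedure, step 3).** Dose rates are fitted, and the area under the fitted curve is taken as the mean absorbed dose. No division by injected activity is stated at this step.

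Neither route mentions a scan just before infusion #6, a subtraction for earlier infusions, or a multi-infusion model. The appendix does not say which injected activity applies at #6, or how the #1 and #6 results are combined into a total.

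**The concern.** A gamma camera cannot tell radium given at infusion #6 from radium still bound after earlier infusions. At infusion #1 there is nothing left over, so total counts divided by the injected activity give the right coefficient. At infusion #6, if bone lesions hold radium, the counts come from six infusions, and the written rule does not separate them.

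Two outputs depend on this. The first is total lesion exposure, the stated purpose. The second is the companion hypothesis that more than 30% of men would have needed a changed external-beam plan, judged against a tumour-dose threshold and normal-organ limits. An inflated lesion dose makes the threshold look met, and an inflated organ dose makes a limit look exceeded, so the net direction for that proportion cannot be known in advance. The size of the residual also depends on each man's dosing dates, which adds schedule noise to an analysis meant to describe variability between patients.

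**Working it through.** **Inputs.** Decay table, 28-day interval and six injections (Section 6.4); scan times (Appendix IX); ordering window and permitted delay (Section 6.11). The documents give no lesion uptake or retention data, so these are assumptions and a range is shown.

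**Step 1: reproduce the table.** A log-linear fit to its 29 factors gives a half-life T = 11.43 d. With the 7-hour time-zone offset that Section 6.4 describes, factor(d) = 2^(−(d + 7/24)/11.43). This gives 0.982 at day 0 and 0.420 at day +14, as printed, and every entry is matched within 0.0006. As a cross-check, Section 6.6 treats 4 months of storage as ">10 half-lives", and 120/11.43 = 10.5.

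**Step 2: residual from one infusion.** r = 2^(−28/11.43) = 0.183, so 18.3% of a fully retained infusion is present when the next is given.

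**Step 3: residual at infusion #6.** With equal activity and uptake, and physical decay only:

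r + r² + r³ + r⁴ + r⁵ = 0.1831 + 0.0335 + 0.0061 + 0.0011 + 0.0002 = 0.224

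The measured activity is therefore 1.224 times the infusion #6 contribution. Residual and new activity decay at the same rate here, so the ratio is the same at every scan and in the fitted integral.

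**Step 4: effect of the denominator.**
- Divided by the #6 activity: 1.224, or 22% too high.
- Divided by all six activities: 1.224/6 = 0.20 of the true per-infusion coefficient.

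Neither reading gives the right value without a residual term.

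**Step 5: sensitivity (excess when divided by the #6 activity).**

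| Change from base case | Excess |
|---|---|
| None | 22.4% |
| Effective half-life 9 d | 13.1% |
| Effective half-life 7 d | 6.7% |
| Effective half-life 5 d | 2.1% |
| Last gap 56 d (28 + 28) | 4.1% |
| Last gap 25 d | 26.9% |
| All gaps 25 d | 28.1% |
| #6 uptake 1.25 times earlier uptake | 17.9% |
| #6 uptake 0.8 times earlier uptake | 28.0% |
| #6 uptake 0.5 times earlier uptake | 44.8% |

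**Step 6: total exposure.** Appendix IX states no summation rule, so two possible ones are shown for the base case, in units of one clean infusion integrated to infinity. The true total is 6.
- Five clean infusions plus the uncorrected #6 area: (5 + 1.224)/6 = 1.037, about 4% too high.
- Six times the mean of the #1 and #6 results: (1 + 1.224)/2 = 1.112, about 11% too high.

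Both percentages refer to the radium part of the dose only.

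**The case against.** The strongest reply is that Appendix IX is silent rather than wrong. A reader might infer that the plan divides by the infusion #6 activity alone. That is the natural reading of a per-infusion coefficient, but the text does not say it. The 3D-RD method is only summarised, with published methods and committee guidance cited behind it, and the study runs under a companion protocol that is not among these documents. A correction could exist there. All of this stands. What remains is that the rule as written gives a wrong #6 coefficient under either denominator, so stating the denominator alone would not cure it.

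On the 3D-RD route, the reply is that residual radium really does irradiate the lesion. That is correct. The area becomes an error only if it is credited to #6 alone, or added to earlier infusions that were already integrated to infinity.

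Three further inferences go beyond the documents:
- **That 22% is a maximum.** It rests on equal uptake and exact 28-day gaps; shorter gaps or lower uptake at #6 raise it.
- **That a comparison of #6 with #1 would show a false rise in uptake.** No such comparison is planned.
- **That men would be misclassified on the adjustment criterion.** The dose map also includes external-beam dose, and radium's share of the total is not given, so no change of classification can be shown.

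Finally, the work is labelled exploratory, is retrospective and leaves treatment unchanged. That limits the weight of the point but does not remove it, since the appendix expects the results to be published.

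**Conclusion.** The concern holds in limited form. Appendix IX applies one rule to both infusions although the #6 images contain radium from five earlier ones, and it gives neither a residual term nor a #6 denominator. The base-case excess is about 22% when the coefficient is divided by the #6 activity. That assumes physical decay only, 28-day gaps, and equal activity and uptake at each infusion. Faster clearance or a late sixth infusion brings it down to a few percent; shorter gaps take it to 27–28%, and lower uptake at #6 can take it further. The half-life comes from the protocol's own table, but retention and uptake are not documented, so the true excess in any man is unknown.

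The 3D-RD area contains the same residual and needs a rule against double counting. The reach is confined to total lesion exposure and the adjustment hypothesis in the companion study. Treatment, the PFS analysis and the sample size are unaffected.

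**What to change.** In Appendix IX:

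1. Define the denominator for the #6 coefficient as the infusion #6 activity.
2. In both the TIAC and 3D-RD routes, subtract at each #6 scan time a residual predicted from the infusion #1 curve and the recorded dates and activities of infusions #1–5.
3. Compute total exposure over the six infusions by superposition, so that no decay is counted twice.
4. Report a sensitivity range: residual by physical decay only, residual at the fitted effective half-life, and no correction. Do not call these bounds. Nothing is measured beyond 48 h or at infusions #2–5, so the truth can lie outside them; if uptake rose during treatment, for example, the subtraction may be too small.

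The cost is a few lines in the dosimetry procedure and a calculation on recorded data. It needs no extra scan and can be applied to images already acquired. The downside is that #6 per-infusion doses become somewhat lower and carry model uncertainty, because a curve observed for two days is projected forward 28 to 140 days.
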